Deep brain stimulation for severe obsessive compulsive disorder: Efficacy and mechanisms of ventral striatum and subthalamic nucleus targets

Protocol December 2012 version 1.1

1. Background

- 1.1. Obsessive compulsive disorder (OCD) has a lifetime prevalence of 1-2 % and is characterised by intrusive unwanted thoughts and compulsive behaviours that vary in intensity, frequency and character. The standard treatment is cognitive behaviour therapy (CBT) and/or serotonin re-uptake inhibitor (SRI) medication but these are ineffective in up to 40% of cases ¹. Symptoms in this treatment-refractory subgroup can be sufficiently severe that patients are unable to perform activities of daily living, sustain work or maintain relationships. The English NHS National Specialised Commissioning Group has commissioned services to provide assessment and intensive CBT and pharmacotherapy for such patients. Although these have good results ^{2, 3} there remains a truly refractory subgroup for whom ablation of the anterior cingulate cortex is an option ⁴. Prospective longitudinal studies of cingulotomy suggest a sustained 2-year response rate of 32% with few adverse events and a concomitant improvement in quality of life ^{5,6}.
- 1.2. Deep brain stimulation (DBS) may improve upon this success rate as the response can be modified following surgery - stimulation can be adjusted to optimise benefits and minimise adverse effects. DBS also has the advantage of reversibility in that stimulation can be switched off if the response is unsatisfactory and electrodes can be removed. Studies which have used similar response criteria to those of tissue ablation implicate two DBS brain targets as being particularly effective - the ventral striatum/ventral anterior capsule (VS/VC) and the subthalamic nucleus (STN). Two studies have found that 56% or 62% of patients respond with VS/VC electrodes stimulating ventral striatal grey matter and adjacent white matter fibres en route to and from medial and orbital frontal cortex ^{7,8}; a third study found 75% responded with STN electrodes stimulating the boundary between associative and limbic grey matter, although the criterion for success was less strict than that of the VS/VC studies ⁹. All three studies additionally found concomitant improvements in everyday function, suggesting that DBS can be considered a promising treatment for severe OCD.
- 1.3. Before DBS for OCD can be introduced into routine clinical practice, further research is required to determine the optimum DBS brain target. It may also be possible to improve upon the degree of response to DBS by understanding more about the mechanisms of action at the two target sites - although two-thirds were considered responders in previous studies, the patients remained symptomatic, being reduced from the 'extreme/severe' to the 'moderate' category ⁷. Furthermore, although CBT will not have previously been effective in these patients, DBS may reduce symptoms enough to enable them to use CBT more effectively and, indeed, the combination may result in a better outcome than DBS alone. To address these questions we have brought together a network of specialist OCD clinicians, leading OCD cognitive neuroscientists and expert DBS clinicians to undertake the first UK study of DBS for severe, medically intractable OCD.

2. Aims and Hypothesis

2.1. The overarching aim is to compare the effects of VC/VS and STN DBS in the same patients. We will test the hypothesis, grounded in cognitive neuroscience, that DBS at both sites is better than either site alone for treating the symptom dimensions of OCD. Specifically, we will employ novel cognitive paradigms and neurophysiological measures of cortical synaptic function to test the hypothesis that VS/VC and STN DBS have different mechanisms of action and that alleviation of OCD symptoms is mediated by improvement in mood/anxiety with VS/VC DBS and by directly interrupting obsessions and compulsions with STN DBS. We will additionally determine whether adjunctive CBT enhances the response to DBS by providing the cognitive and behavioural skills to optimise symptom management and daily function.

3. Scientific Rationale

3.1. The VS/VC and STN are both ‘stations’ in the neural circuitry thought to be dysfunctional in OCD. The pre-eminent neurobiological model of OCD implicates abnormalities of orbitofrontal cortex (OFC), anterior cingulate cortex (ACC) and ventral striatum¹⁰. These structures are integral to limbic cortico-striatal-thalamo-cortical circuitry whereby cortical outputs synapse successively in ventral striatum, ventral pallidum and mediodorsal nucleus of thalamus before projecting back to cortex; within this system, the pallidum projects to thalamus either directly or indirectly via the subthalamic nucleus. It is therefore possible that the observed clinical improvement in OCD with DBS is due to high frequency electrical stimulation disrupting abnormal activity in the limbic circuit and that this can be obtained at either of the two target sites. However, the ventral striatum and STN are thought to have separate functions, important in different ways for modulating information processing in the cortico-striatal-thalamo-cortical circuitry essential for the control of behaviour. Thus, although both VS/VC and STN DBS affect the same neural circuit, their mechanism of action may be quite different and stimulation at each of these locations may have unique effects on the symptom dimensions of OCD.

3.2. Evidence for different clinical effects comes from findings that VS/VC DBS produced early and sometimes dramatic mood elevation and anxiety reduction prior to improvement in obsessions and compulsions whereas STN DBS, while diminishing obsessions and compulsions, had no effect on emotion^{7,9,8}. This observation is relevant because mood and anxiety are significant symptom dimensions in OCD and increases or decreases in the severity of anxiety or depression are generally accompanied by parallel changes in the severity of obsessions/compulsions¹¹. The ventral striatum, as well as being the first target of OFC/ACC cortical outputs, receives inputs from amygdala and midbrain dopaminergic neurones, which together provide the emotional and motivational impetus for goal directed behaviour¹². The ventral striatum is therefore in a unique position, via its involvement in limbic cortico-striato-thalamo-cortical circuitry, to influence the cognitive and motor processing in parallel circuits which is preparatory for action selection and ultimately

manifest in thoughts and actions ¹². Denys and colleagues ⁸ proposed that VS/VC DBS influences OCD symptoms via its effect on anxiety and mood. Taking this further, we hypothesize that stimulation of ventral striatal neurones influences reinforcement learning and emotion processing thereby improving mood and reducing anxiety and resulting in a decrease in the intensity of obsessions and compulsions.

- 3.3.** STN DBS on the other hand may have a more direct effect on obsessions and compulsions. The limbic STN, like the ventral striatum, is in a unique position to influence behavioural outputs of cortico-striatal-thalamo-cortical circuitry. This is because the STN receives a direct projection from right inferior frontal cortex which acts as a 'hyperdirect pathway', activation of which overrides neural processing in the direct cortico-striato-pallido-thalamic pathway. This results in the inhibition of ongoing, planned acts and thoughts ¹³. We therefore hypothesise that, via this inhibitory mechanism, stimulation of STN neurones enables OCD patients to interrupt their repetitive thoughts and actions resulting in a decrease in obsessions and compulsions.
- 3.4.** Accordingly, DBS at both sites, because of different mechanisms of action, is predicted to be clinically more effective than stimulation of either site alone. It also follows that if there are two mechanisms mediating OCD improvement, this should be evident in different patterns of cognitive and neurophysiological effects following DBS. In the proposed study we will test these predictions clinically and experimentally by using paradigms designed to distinguish the two hypothetical mechanisms of action.
- 3.5.** The main aim of CBT is to enable OCD patients to obtain greater control over behaviour so that they can inhibit their repetitive thoughts and acts and switch to more meaningful alternatives. One abnormal mechanism contributing to such cognitive inflexibility is thought to be blunting of the value of positive and negative reinforcement normally used to guide responses and dependent on intact OFC-striatal neural circuitry ¹⁴. Dysfunction of this cognitive control system has been shown in first-degree clinically unaffected relatives of OCD patients thus confirming this mechanism as a neurobiological phenotype of OCD ¹⁵. It is therefore hypothesised that DBS of VS/VC will improve the processing of reinforcing stimuli and that this will result not only in elevation of mood and reduction in anxiety but also in increased cognitive flexibility. We will test this by measuring the effectiveness of VS/VC DBS on clinical measures of mood, anxiety, obsessions and compulsions and relate these to changes in reinforcement learning and emotional processing using cognitive tasks sensitive to OCD which measure the ability to respond appropriately to reinforcing contingencies.
- 3.6.** Attentional processes are also thought to contribute to impaired behavioural control in OCD. Being able to stop or inhibit planned acts when environmental circumstances change depends on the function of the right inferior cortical-STN hyperdirect pathway and can be operationalised by measuring the stop signal reaction time (SSRT) ¹⁶. The finding of specific prolongation of SSRT in OCD patients and their unaffected first-degree relatives suggests that this cognitive abnormality is also a phenotype of OCD ¹⁷. Although the neural substrate of this mechanism does not involve the limbic cortico-striato-pallido-thalamic circuit,

recent evidence suggests that neural systems outside this circuitry, involving the right inferior frontal cortex, are impaired in OCD¹⁰. We therefore hypothesise that STN DBS allows inhibition of repetitive thoughts and acts in OCD by facilitating the action of the hyperdirect pathway from the right inferior frontal cortex to STN. We will test this by measuring the effectiveness of STN DBS on obsessions and compulsions and relate these to changes in SSRT and performance on other tasks sensitive to right inferior frontal cortex function which measure the ability to inhibit pre-potent tendencies.

- 3.7.** OCD symptoms and cognitive impairment may be mediated by abnormal cortical excitability due to aberrant long term depression (LTD) synaptic plasticity¹⁸ and/or reduced GABA-mediated intracortical inhibition¹⁹. Transcranial magnetic stimulation (TMS) can be used to measure these neurophysiological processes safely in patients undergoing DBS and both abnormalities have been shown to normalise following DBS in other disorders²⁰. We will use TMS to assess these neural processes before and after DBS in OCD patients and test for whether there are differential changes from the two DBS sites and whether combined VS/VC and STN DBS produces more vigorous improvements compatible with our hypothesis concerning the superior clinical effects of this condition. We will measure intracortical inhibition not only at rest but also during the anticipation of reinforcement, previously shown to affect motor cortex excitability²¹ and which we predict will be specifically affected by VS/VC DBS.

4. Research Programme

- 4.1. Subjects:** Six patients will be recruited from the OCD National Specialist Commissioned Services of [name], South West London and St George's Mental Health Trust (SWLSG MHT) and [name], Herts Partnership NHS Foundation Trust (HPFT).
- 4.2. Inclusion criteria:** The inclusion criteria have been designed to be consistent with previous OCD DBS studies and to ensure that patients have not responded in a useful and sustained manner to either modifications of medication or any form of CBT⁴.

Patients must have undergone intensive treatment and have demonstrable treatment resistance as defined by:

- a. At least two SRIs for a minimum of 12 weeks at optimal British National Formulary (BNF) doses.
- b. Augmentation of SRI treatment with antipsychotic drugs administered at maximally tolerated doses or by extending the SSRI dose beyond BNF limits.
- c. Two trials of CBT of at least 10 hours.
- d. Failed inpatient treatment for OCD.

Patients must also satisfy the following criteria:

- e. Age > 20 years.

- f. Confirmation of a primary diagnosis of obsessive compulsive disorder (ICD10 F42.0—F42.9).
- g. Duration of illness of at least 10 years.
- h. At least 2 years of unremitting symptoms despite intensive psychopharmacological and psychological treatment or failure to sustain, over a 3 month period, a response to inpatient psychological treatment by at least 33% with accompanying optimised pharmacological therapy.
- i. A minimum score of 32 on Yale Brown Obsessive Compulsive Scale (YBOCS) 22 thus constituting profound illness and a maximum score of 50 on the DSM IV General Assessment of Function Scale (GAF).
- j. Ability to provide sustained informed consent.

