Stage 6: Randomisation and initiation of STN or VS/VC DBS for 12 weeks. The stimulation parameters will be adjusted on a daily basis until judged optimal (see below for details). Optimisation process will also be guided by a modified Visual Analogue Scale (VAS) to measure urges to perform compulsions and fluctuations in the mood. Specific behavioural challenges will be designed for each patient in accordance with their previous clinically documented symptoms of OCD and will be administered by the research psychiatrist during the optimisation process to elicit obsessive and compulsive responses. The strength and

intensity of these responses will be measured with modified Visual Analogue Scales by both patient and the psychiatrist. This may take up to 2 weeks; patients will have the option of being admitted to Hughlings Jackson ward or attending as a day case. If the latter, they may stay overnight at a local hotel with a carer (according to standard NHHN day unit procedures) or stay overnight at home if practical. Stimulation optimisation period will not be included in the 12 weeks allocated to the stimulation stage.

Stage 7: The current stimulation will be switched off for 24 hours and the alternative site stimulated for 12 weeks. The same procedures and options for hospital attendance in Stage 6 will apply.

Stage 8: The current stimulation will be switched off for 24 hours and both sites will be stimulated for 12 weeks. The same procedures and options for attendance in Stage 6 and 7 will apply.

Stage 9: Patients will continue with DBS at their best DBS site(s) and settings. This may require a further admission for stimulus/site adjustment as above if the current stimulation is not judged to be optimal.

Stage 10: After 12 weeks stabilisation on the best DBS settings and site, patients will be offered inpatient cognitive behavioural therapy at SWLSG MHT for 12 weeks.

6. Study procedures and assessments

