6.7. TMS assessments

During TMS electromyography recordings will be made from abductor pollicis brevis (APB) and first dorsal interosseus (FDI) muscle using surface electrodes. Signals will be amplified and band pass filtered at a sample rate of 5000 Hz. TMS will be applied using a 70 mm figure of eight coil and Magstim 200 generators.

- a. **Cortical plasticity assessment:**
Paired associative stimulation (PAS) after localisation of the “hotspot” the resting (RMT) and active (AMT) motor thresholds will be determined. At 0.5, 15 and 30 min after PAS, we will obtain a stimulus response curve; MEPs will be recorded at each intensity from RMT-10% maximum stimulator output to RMT+30%. The inhibitory PAS10 paradigm (200 pairs, at 0.25 Hz) will be used. Median nerve stimulation (constant current generator) at 3x perceptual threshold intensity (duration 0.2 ms) will be delivered before TMS over the APB “hotspot” (intensity at 1 mV MEP prior to the start of the procedure).
- b. **Intracortical inhibition (SICI) assessment:**
TMS will be delivered to the FDI “hotspot”. The first, conditioning-stimulus, will be set at 80% AMT and the second, test stimulus at a 1 mV MEP level when given alone. Interstimulus intervals of ^{2,3} will be explored (n=12 per interval, randomly intermixed). SICI will be calculated by pooling 2 and 3 ms data and expressed as the ratio between conditioned and unconditioned trials. SICI will also be combined with a reward paradigm ²¹.

6.8. Timing of assessments and procedures: *(Please also see Table 1)* All assessment will be performed prior to surgery. Cognitive and TMS assessments will be performed additionally at the end of each of the 3 DBS periods, at the end of the optimisation of DBS period and at the end of CBT. Where possible, alternative forms of the tests will be used to avoid practice effects. Clinician-based clinical assessments will additionally take place monthly or more often if judged necessary. Patient self-report assessments will additionally take place at the end of each of the 3 DBS periods, at the end of the optimisation of DBS period and at the end of CBT.

7. Data Analysis

7.1. Descriptive analysis will be used to quantify changes in clinician-related YBOCS scores by using visual plots and specifying means and 95% CIs or medians and IQRs. We will then compare these changes using Friedman's ANOVA to account for the lack of independence between observations.

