7.2. The primary efficacy measure will be the clinician-rated YBOCS total scores. Friedman's ANOVA across all 4 conditions (pre-op baseline and after 3 months DBS in STN, VC/VS and STN+VC/VS) will be performed. A categorical efficacy measure, responder/non-responder status after each 3 month DBS block will be defined as $\geq 35\%$ decrease in YBOCS and will be analysed with the McNemar exact test for comparison of the VC/VS and STN DBS conditions. Descriptive analysis in addition to Friedman's ANOVA will also be used to analyse the mechanistic hypotheses on the following variables: MADRS, SSRT, ID/ED, probabilistic reversal learning, affective go/no go scores and TMS. The additional benefit of CBT will be analysed using Wilcoxon matched-pairs before and after CBT.

7.3. These data will also allow an estimate of mean effect and variance of the main effect to be made to allow a sample size calculation for a future fully powered trial.

8. Ethics and patient safety

8.1. Clinical care: All patients will be under the care of NHS OCD specialised services and their local community mental health team (CMHT). Consistent with the existing nationally commissioned clinical pathway, all potential participants will be offered the choice of anterior cingulotomy or DBS. Although this study is designed to examine the effect of DBS and not to compare the two procedures, adopting the standard care pathway will ensure that existing robust governance and consent procedures will be applied for all participants.

8.2. Monitoring for potential DBS adverse effects: The published risks of STN and VC/VS stimulation are mainly hypomania and anxiety, which are voltage dependent and 8, 9 and either self-limiting or resolved by modifying the stimulation settings. Clinical worsening, including lowering of mood has also been reported after stimulation is switched off. To

monitor and manage any adverse effects, the following procedures will be in place for each patient:

- a. Prior to surgery, in conjunction with the responsible OCD clinician [name] the study research clinician will contact the CMHT, speak to the responsible consultant and key worker about the study and provide regular progress reports.
- b. Patients will remain in hospital following changes in DBS for at least 24 hours following the final stimulation adjustment.

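### The planned analysis of the combined condition cannot tell an added benefit of dual stimulation from patients differing in which single site helps them

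*Protocol*

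**What the plan says.** Section 2.1 gives the hypothesis as "that DBS at both sites is better than either site alone for treating the symptom dimensions of OCD". Section 3.4 gives the reason: "DBS at both sites, because of different mechanisms of action, is predicted to be clinically more effective than stimulation of either site alone".

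Section 7.2 sets the measure: "The primary efficacy measure will be the clinician-rated YBOCS total scores". The analysis of that measure is "Friedman's ANOVA across all 4 conditions (pre-op baseline and after 3 months DBS in STN, VC/VS and STN+VC/VS) will be performed". Section 7.1 adds description of YBOCS change "by using visual plots and specifying means and 95% CIs or medians and IQRs". Responder status (a fall of at least 35%) is defined after each block, but the only test named for it "will be analysed with the McNemar exact test for comparison of the VC/VS and STN DBS conditions".

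No comparison of combined with STN, of combined with VC/VS, or of combined with the patient's own better single site is named. The idea of a patient-specific best site does appear in the protocol, as a clinical step in section 5.4, Stage 9: "Patients will continue with DBS at their best DBS site(s) and settings".

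**The concern.** The Friedman test is an omnibus test. It asks whether any of four conditions differs, and one of the four is the untreated baseline. A fall from baseline under stimulation can produce a small p-value whether or not the combined block beats a single site.

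The ordering of conditions is ambiguous too. Friedman ranks within patients but sums the ranks per condition. If some patients respond mainly to STN and others mainly to VC/VS, which two separate mechanisms would allow, then each single-site block mixes good and poor responses. The combined block contains every patient's helpful site. It then has the best mean and the best rank sum even if no patient does better with both sites on than with the better one alone.

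At stake is the reading of the main hypothesis. The same summary table would fit two conclusions: that stimulating both sites adds benefit, or that each patient needs the right single site. Every patient receives all three conditions, so the design holds the data to help separate the two. The stated analysis does not use them.

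**Working it through.** The protocol gives no power, alpha or effect figure to reproduce. The check is a counterexample, followed by a look at how far its size depends on assumptions.

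**1. Counterexample (assumed scores).** Six patients (section 4.1), baseline YBOCS 36 (assumed; the entry minimum is 32). Three score 20 on STN and 32 on VC/VS, three the reverse, and all score 20 on both. The gain over the patient's own better site is 20 − 20 = 0 in all six.

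- Means: baseline 36; STN (3×20 + 3×32)/6 = 26; VC/VS 26; combined 20.
- Ranks within a patient (1 = lowest): the two scores of 20 share 1.5, the 32 gets 3, the 36 gets 4. Rank sums: baseline 24, STN 3×1.5 + 3×3 = 13.5, VC/VS 13.5, combined 9.
- Friedman, four conditions: 12/(6×4×5) × (24² + 13.5² + 13.5² + 9²) − 3×6×5 = 102.15 − 90 = 12.15. Tie correction 1 − 36/360 = 0.9. Q = 12.15/0.9 = 13.5, 3 df, p = 0.004.
- Friedman, three DBS conditions only: 12/(6×3×4) × (13.5² + 13.5² + 9²) − 3×6×4 = 74.25 − 72 = 2.25. Tie correction 1 − 36/144 = 0.75. Q = 2.25/0.75 = 3.0, 2 df, p = 0.22.
- Responders: 36 to 20 is a fall of 44%, 36 to 32 a fall of 11%. McNemar for VC/VS versus STN has 3 against 3 discordant patients, p = 1.
- Combined versus either single site: the mean difference is 20 − 26 = −6 points, but only three patients differ. The smallest two-sided exact Wilcoxon p is 2/2³ = 0.25 (2/2⁶ = 0.031 if all six differed).

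So much of the significance comes from baseline, and the 6-point ordering comes entirely from differences between patients.

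**2. Size with the protocol's response rates.** Section 1.2 cites 56% or 62% for VS/VC and 75% for STN, the latter under a less strict criterion. The overlap of responders is not given. Share responding to at least one site, using 62% and 75%:

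- full overlap: 75%, no excess over STN;
- independence: 1 − 0.38×0.25 = 90.5% (with 56%: 1 − 0.44×0.25 = 89.0%);
- least overlap: 100%.

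Under independence this means 6×0.905 = 5.4 responders on combined, against 6×0.75 = 4.5 on STN and 6×0.62 = 3.7 on VC/VS, with no added effect in anyone.

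**3. Size on the score scale (assumed spread).** Suppose true site effects are normal with equal means, SD 6 and within-patient correlation ρ. The better of the two exceeds either one by SD×√((1−ρ)/π) on average: 3.4, 2.4 and 1.5 points for ρ = 0, 0.5 and 0.8. With rating noise SD 2 or 3, and combined set equal to the better site, combined has the lowest mean in 64% to 89% of simulated six-patient trials. If patients do not differ by site, three equal conditions give about 33%, which is chance.

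**4. Behaviour of a comparison with the better site.** Under the assumptions of step 3:

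- Better site chosen at month 2, compared at end of block: bias about 0.2 to 0.5 points towards combined, standard error 1.2 to 1.8.
- Lower of the two end-of-block scores as comparator: bias about 0.2 to 0.8 points against combined. If the two sites are truly equal, it is noise SD/√π = 1.1 to 1.7 points against.

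**The case against.** Several points on the other side are sound and limit the concern.

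- A reader might infer that section 7.2 formally tests combined against each single site and would wrongly declare dual stimulation superior. It names no such contrast. In the illustration neither the three-condition test (p = 0.22) nor a paired test (p no lower than 0.25) would declare it. The problem lies in what is read from the omnibus p-value and the ordering of means.
- A reader might also infer that the plan would give a false answer to section 2.1. That is too strong. The hypothesis can fairly be read at group level, and section 5.2 puts the purpose as finding the best site or sites for practice. If patients differ unpredictably, combined stimulation really does outperform giving everyone the same single site.
- The paired responder table behind McNemar and the plots in 7.1 would show a split by site in six patients. This helps, but the table as used leaves out the combined block.
- Mechanism is not inferred from YBOCS alone: section 7.2 also analyses mood, cognitive and TMS measures. These speak to mechanism, but not to whether a patient gains beyond the better site.
- Section 7.3 speaks only of a main effect and does not say which. The documents do not show that an inflated combined-versus-single figure would go into the future sample size.
- Follow-up contrasts may stand in an analysis plan that is not shown. The point is therefore confined to what 7.2 fixes: an omnibus test with baseline as the only named test that includes the combined condition.

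**Conclusion.** The concern holds in limited form. As written, a significant Friedman test or a best mean or rank sum for the combined block does not show that dual stimulation adds benefit. Either can arise from the fall from baseline together with differences between patients in which site helps, with zero gain over anyone's better site.

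That this can happen rests only on the definition of the test. How large it would be rests on assumptions: from no excess over STN (full overlap of responders) to 25 percentage points (least overlap), or 1.5 to 3.4 YBOCS points for an assumed SD of 6 and correlations of 0.8 to 0. The documents give neither overlap nor spread, so no single figure should be quoted as the expected error.

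This is an inexpensive improvement that would limit what the trial may conclude about section 2.1. The combined block also always comes last, which is a separate issue that paired differences do not remove.

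**What to change.** In section 7.2:

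1. State the within-patient end-of-block YBOCS differences, combined minus STN and combined minus VC/VS, as the group-level assessment of the hypothesis in 2.1.
2. Add a prespecified supportive analysis: the six differences of combined minus the patient's own better single site, with an interval. Choose the better site from the month-2 rating, so that the end-of-block comparator is not selected on its own noise. Use the lower of the two end-of-block scores as a sensitivity analysis.
3. Show the paired responder table (both single sites, STN only, VC/VS only, neither) alongside response on combined.
4. State that a gain beyond the better single site is claimed only if the supportive analysis agrees. Otherwise report group-level superiority that may reflect differences between patients in which site works.

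The cost is a few sentences, with no new patients or visits. This takes the monthly clinician assessments in section 6.8 to include the YBOCS. The downsides are a less favourable combined effect, low precision with six patients, and residual selection bias: towards combined with month-2 selection, against it with the lower-of-two version. Because that bias can be as large as the artefact when the sites act alike, both versions should be reported with the bias disclosed, and neither should serve as the sole pass/fail rule.

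### Sections 3.5 and 3.6 promise to relate clinical change to cognitive change, but the variable-by-variable analysis fixed in 7.2 cannot estimate that relation

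*Protocol*

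**What the plan says.** Section 2.1 words the hypothesis as mediation: "alleviation of OCD symptoms is mediated by improvement in mood/anxiety with VS/VC DBS", and direct interruption of obsessions and compulsions with STN stimulation.

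Sections 3.5 and 3.6 then say how each mechanism will be tested. For VS/VC, clinical effects on mood, anxiety, obsessions and compulsions are measured, and the investigators will "relate these to changes in reinforcement learning and emotional processing using cognitive tasks sensitive to OCD". For STN, section 3.6 says "We will test this by measuring the effectiveness of STN DBS on obsessions and compulsions and relate these to changes in SSRT" and to other tasks of inhibition.

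Section 7.2 names the analysis: "Friedman's ANOVA will also be used to analyse the mechanistic hypotheses on the following variables: MADRS, SSRT, ID/ED, probabilistic reversal learning", followed by affective go/no go and TMS, with descriptive analysis alongside. Section 7.1 describes descriptive analysis, for YBOCS, as "by using visual plots and specifying means and 95% CIs or medians and IQRs". The other tests in section 7 are Friedman on YBOCS across four conditions, McNemar on responder status (VS/VC against STN) and Wilcoxon before and after CBT.

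**The concern.** Sections 3.5 and 3.6 define a test that joins two measures in the same patients. Section 7.2 fixes a method that takes each measure separately. This is more than detail left to a statistical analysis plan: the protocol does choose a method for the mechanistic hypotheses, and that method does not answer the question set.

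YBOCS and SSRT could both improve on average under STN stimulation although the patients whose inhibition improved were not those whose OCD improved. Under 7.2 as written, such parallel shifts could be reported as support for the inhibition mechanism, and the analysis named there would not reveal the mismatch.

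**Working it through.** The protocol gives no figure for this relation and no power or alpha, so there is nothing to reproduce. Two-sided 5%, normal data (for the power figures and the Pearson and Fisher results) and the true correlations used below are assumptions.

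**1. The passages side by side.**
- STN: 3.6 relates the effect on obsessions and compulsions to change in SSRT and other inhibition tasks; 7.2 has Friedman on SSRT and on ID/ED, each alone.
- VS/VC: 3.5 relates mood, anxiety, obsessions and compulsions to reinforcement learning and emotional processing; 7.2 has Friedman on MADRS, reversal learning and affective go/no go, each alone. No anxiety scale is listed in 7.2, although 6.5 collects two (HAS and BAI).
- Section 7 contains no correlation, regression or other joint analysis of a clinical and a cognitive measure.

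**2. Can separate Friedman tests carry the relation?** Take six patients (4.1) and the four conditions that 7.2 states for YBOCS. Invent falls d in YBOCS of 4, 7, 10, 13, 16, 19 and in SSRT of 5, 15, 25, 35, 45, 55, with condition values b, b - d, b - 0.8d and b - 1.2d for patient baseline b. Every patient ranks the conditions 4, 2, 3, 1, so the rank sums are 24, 12, 18 and 6.
- Friedman statistic = 12/(6 x 4 x 5) x (24² + 12² + 18² + 6²) - 3 x 6 x 5 = 0.1 x 1080 - 90 = 18.0; on 3 df, p = 0.00044. This holds for each variable.
- Patients matched: the two changes correlate at rho = +1. SSRT patients reversed: rho = -1. Both Friedman statistics remain 18.0.

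The tests are the same under opposite relations, so they carry no information on it.

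**3. What a patient-level change-on-change analysis gives with n = 6.**
- Spearman, exact over all 720 permutations: |rho| ≥ 0.886 gives p = 0.033; the next lower value, 0.829, gives p = 0.058.
- Pearson: critical |r| = t/√(df + t²) = 2.776/√(4 + 2.776²) = 0.811.
- Fisher 95% interval, tanh(atanh r ± 1.96/√3): r = 0.5 gives -0.52 to 0.93; r = 0.7 gives -0.26 to 0.96; r = 0.8 gives -0.03 to 0.98.
- Simulated Spearman power: about 10%, 21% and 32% at true correlations 0.5, 0.7 and 0.8.
- For 80% power by Fisher z, N is about 30, 14 and 10 at 0.5, 0.7 and 0.8.

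**4. A pooled within-patient regression over the three DBS conditions.** There are 6 x 3 = 18 observations. Removing 6 patient effects and one slope leaves 11 df (critical |r| 0.553). Adding two condition terms leaves 9 df: 2.262/√(9 + 2.262²) = 0.602.

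Simulation with YBOCS and SSRT unrelated given condition, but both shifted by 2 within-patient SD under STN and combined stimulation relative to VS/VC (assumed):
- patient effects only: an association is declared in about 61% of runs;
- patient plus block number: about 45 to 50%;
- patient plus condition: about 5%.

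With condition included, power is about 54% at a within-patient r of 0.6 and 91% at 0.8.

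**The case against.** The strongest reply is that the prediction separating the two mechanisms is the one in 3.4 and 6.6: different patterns of effect, with SSRT and ID/ED more sensitive to STN and the other two tasks to VS/VC. Condition comparisons within each variable can address that. This stands. A reader might infer from the gap that the mechanistic hypotheses go untested altogether; the protocol does not support that. What is missing is the further test that 3.5 and 3.6 describe.

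A second reply is that the wording sits in a rationale section and names no statistic. But both sections say the hypothesis will be tested this way, and 7.2 claims to analyse the mechanistic hypotheses without it.

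A third is that six patients are too few, that the analyses are secondary, and that the study is meant to inform a future fully powered trial. This also stands: it limits the fix to an exploratory estimate and keeps the point well short of the primary analysis. It does not reconcile the sections.

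It is also tempting to think that a within-patient regression across conditions would settle the question with good power. Without a condition term it would present shared group shifts as a within-patient association, which is the very error at issue. Pooling also gives no site-specific estimate.

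**Conclusion.** The point holds as an inconsistency between the stated test and the stated analysis. Under the analyses named in section 7, the relation between clinical and cognitive change is not estimated, and the method in 7.2 cannot estimate it. A statistical analysis plan that is not shown might add it, so a reader should not conclude that it will never be estimated. The primary YBOCS comparison and the differential-pattern prediction are not affected.

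The loss is qualitative: Friedman results are identical at rho = +1 and rho = -1. What can be recovered is modest. With six patients a site-specific correlation is descriptive, and an association, even a strong one, would not by itself establish the mediation worded in 2.1. The power figures rest on assumed normal data, two-sided 5% and assumed true correlations. The false-association rates also rest on the assumed 2 SD shifts; at 1.5 SD they are about 31% with patient effects only and 23 to 25% with block added.

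**What to change.** Add to 7.2 an exploratory patient-level analysis, by site, of change from pre-operative baseline to the end of the relevant DBS block. For each pair give a paired plot and the Spearman correlation with its interval:
- under STN: YBOCS change with change in SSRT and in ID/ED (2 pairs);
- under VS/VC: change in YBOCS, MADRS and one named anxiety scale with change in probabilistic reversal learning and in affective go/no go (3 x 2 = 6 pairs).

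If a pooled regression across the three DBS conditions is also wanted, specify both patient and condition as fixed effects (9 df, critical |r| about 0.60).

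State that parallel group shifts alone will not be reported as evidence of mechanism, and that these estimates are imprecise and hypothesis-generating.

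The cost is a short paragraph and eight correlations on data that 6.8 already schedules at baseline and at the end of each DBS period. The downside is wide intervals and several estimates from six patients, so isolated small p-values should carry little weight. If the investigators prefer not to add this, reword 2.1, 3.5 and 3.6 so that they claim only a comparison of patterns across sites, not a test of the relation.
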